**The reliability and validity of the PortionSize™ and
MyFitnessPal© apps (Study 1: Laboratory-based evaluation).**

NCT 04700904

Approved: December 3, 2020

Title: The reliability and validity of the PortionSize and MyFitnessPal apps (Study 1: Laboratory-based evaluation).

Principal Investigators: [name].; [name].

Co-Investigator: [name], [name].

Protocol Version Date: December 1, 2020

Background

Accurately quantifying food intake is vital to promoting health and reducing chronic disease risk. Food intake encompasses energy intake, nutrient intake (macronutrients, micronutrients, vitamins, minerals), and intake of various food groups (e.g., fruits, vegetables), and thus reflects the nutritional status of individuals. Nutrition affects disease risk, including risk of developing obesity,¹ diabetes,² and cancer,³ all of which negatively affect the United States (U.S). Nonetheless, accurate assessment of food and nutrient intake has remained challenging, despite an improvement in methods. Self-report methods, namely food records, are a mainstay of nutritional epidemiology research,⁴ with food recall being another popular method.⁵ These methods rely on the participant to accurately estimate portion size and, for food recall, remember what was consumed. The accuracy of these methods have been questioned⁶⁻⁹ and the problems with human recall have been comprehensively outlined.¹⁰ As a result, there remains a significant need for methods that are sufficiently accurate to provide researchers with good outcome data and to guide health promotion efforts.

The PortionSize™ app was designed by our laboratory to overcome the limitations outlined above, and to guide users to follow specific diets. PortionSize relies on users capturing images of their food selection and waste. Food intake data are immediately provided since the user relies on built in tools, including templates, to estimate portion size. However, despite promising early indications, the PortionSize app has yet to be fully validated. Determining the accuracy of PortionSize is vital before users can utilize the app to obtain immediate feedback about their food intake. We accordingly aim to test the validity of PortionSize during two buffet meals in a controlled laboratory setting and compare this to another app that has been adopted widely - MyFitnessPal®, which is an electronic food record.

Methods

Study Design

We will recruit adults to use the PortionSize app or the MyFitnessPal during laboratory-based simulated meals.

Participants and Recruitment

We will recruit 43 adults (approximately equal proportion of men and women) who will be randomly assigned in approximately a 1:1 ratio to use PortionSize at the first visit (and MyFitnessPal at the second visit), or MyFitnessPal at the first visit (and PortionSize

at the second visit). We expect to enroll an approximately equal number of participants with body mass indexes (BMI; kg/m²) between 18.5 to 25; 25 to 30; and 30 – 50kg/m². Recruitment will be stratified based on sex and body mass index.

- Inclusion criteria include:
 - Male or female, age 18-70 years
 - Body mass index (BMI) 18.5-50 kg/m²
 - Ownership of an iPhone model 6s or later, which the participant is willing to use for the study
 - Access to Apple ID, password, and email address and willing to use them in the course of the study
 - Willing to use data and any accompanying charges as part of study participation
 - Willing to be re-contacted for future research and/or follow-up
- Exclusion criteria include
 - Center employee, as previous reviewers argued that they are not representative of the community
 - Any condition or circumstance that could impede study completion

Procedures

Screening visit/Study Visit 1

In the screening visit, written informed consent will initially be obtained. We will then obtain:

- Demographics: age, race, ethnicity, sex, employment, income, marital status, education level (Appendix A: Lifestyle, Demographics, and Health Questionnaire)
- Anthropometrics: height, weight, and BMI

On being deemed eligible, in this within subjects design, participants will be randomized to use either PortionSize or my MyFitnessPal at this first visit, with the other app being used at the second visit. They will receive training on the app that they will use that day to subsequently rate a meal. Training will span up to ~45 minutes.

Participants will then estimate food intake from a simulated lunch meal; i.e., they will not eat food during the meals. The meal will consist of at least three foods, one calorie containing beverage, and may contain a vitamin and/or supplement. Participants' energy requirements will be calculated using sex-specific formulas. Energy requirements will be multiplied by 1.3 and the food selection for the simulated test meal will include 30% of this value, which represents a typical lunch. Plate waste will be determined at the individual food item level and will range between 0% and 100%, but the distribution will be skewed to the lower end such that mean plate waste is ~5% of foods provided, which is slightly higher than actual plate waste from our free-living data

(~3%).¹¹ Simulated food provision and plate waste will be covertly weighed, and simulated food intake calculated by difference.

When participants use PortionSize, they will be instructed to use PortionSize to estimate food provision and plate waste. PortionSize will then calculate food intake, with energy intake being the primary outcome variable. PortionSize will also transfer the food images to the Food Photography Application for expert rater analysis, and these are secondary outcome data. When participants use MyFitnessPal, they will enter estimated food intake into the app.

Near the end of the visit where participants used the MyFitnessPal app, they will complete the MyFitnessPal User Satisfaction Survey (Appendix B) and the MyFitnessPal Computer System Usability Questionnaire (MyFitnessPal CSUQ) (Appendix C) to quantify satisfaction and ease of use of the MyFitnessPal app. The CSUQ is a standardized, reliable, and valid questionnaire originally designed to evaluate computer programs^{12,13} that has been used to quantify the usability of mobile phone apps.^{14,15} Similarly, at the end of the visit where they used the PortionSize app, they will complete the PortionSize User Satisfaction Survey (Appendix D), as well as the PortionSize CSUQ (Appendix E). Additionally, only after the visit that includes the PortionSize app, participants will complete a modified version of a self-administered food frequency questionnaire (Appendix F, Diet History Questionnaire, Version 3.0 or the DHQ-III).¹⁶ Specifically, the DHQ-III was modified such that participants will report the presence of vitamins and supplements during the test meal. Thus, only those items (vitamins and supplements) of the DHQ-III will be administered, and the instructions will ask participants to note if those items were present in the test meal.

Study Visit 2

Participants will return within approximately three to 14 days to be trained on the app not used at the first visit. They will then estimate food intake from another simulated lunch meal. This will be conducted exactly as Study Visit 1. Participants will then complete either the PortionSize User Satisfaction Survey or the MyFitnessPal User Satisfaction Survey, depending on which app they used during Study Visit 2. They will also complete either the PortionSize CSUQ or the MyFitnessPal CSUQ.

Participants then will complete an the User Preference Survey (Appendix G) to determine which app (PortionSize or MyFitnessPal) they prefer, think is most accurate, etc.

Outcome measures

The **primary analyses** assessing equivalence between PortionSize and the criterion measures (and MyFitnessPal and the criterion measures), will rely on equivalence testing using the Two One-side T-test (TOST)^{17,18} method. The criterion measure is directly weighed foods from the simulated lunch meal. Differences in the observed error from PortionSize and MyFitnessPal will be compared with dependent t-tests, with error calculated as the difference between each experimental method and the criterion variable (e.g., energy intake values from PortionSize minus energy intake values from

weighed foods). These procedures will also produce results indicating if the error from each method differs from zero. Subsequent regression-based **exploratory analyses** will determine if error from the apps varies by body mass (kg, BMI), age, or sex; and will evaluate differences in user satisfaction and preference between the apps. Bland-Altman analysis¹⁹ will be used to test for differences in error variance over levels of the variable being measured (e.g., food intake).

Thus, primary endpoints will be:

- Energy intake (kcal)
- User satisfaction and usability of the app

Secondary endpoints will be:

- Nutrients (e.g., fat, carbohydrate, and protein) and food groups (PortionSize only) intake
 - Only PortionSize has the ability to provide output in food groups due to the link with the FNDDS database.

Exploratory endpoints include the modified Dietary History Questionnaire (DHQ) as a comparator for the possible dietary supplement. This specific addition was not an outcome included in the grant and was added post award.

Schedule of procedures

The schedule of procedures is outlined below:

Procedure	Screening and Study Visit 1	Study Visit 2
Informed Consent	X	
Demographics, Anthropometrics, Eligibility Evaluation	X	
Randomization (to use PortionSize or MyFitnessPal first)	X	
Training on PortionSize or MyFitnessPal app	X	X
Use of app during simulated laboratory-based meals	X	X
User Satisfaction Survey, CSUQ	X	X
Modified Dietary Questionnaire (DHQIII ¹⁶)	PortionSize visit only	PortionSize visit only
User Preference Survey		X

The screening portion of the first visit will last approximately 60 minutes. The remainder of Study Visit 1 and Study Visit 2 will last approximately 120 minutes.

Power calculation

We will recruit 43 participants and we are powered even if we experience attrition of up to 10%, resulting in 39 participants finishing both visits. Estimated food intake values from the PortionSize (and MyFitnessPal) will be compared to directly weighed values. Equivalence tests that follow the Two One-sided T-test (TOST)^{17,18} method will be used with alpha = 0.05 and specified acceptable lower and upper bounds of equivalence (error reflects the difference between weighed intake and estimates from either PortionSize or MyFitnessPal). Equivalence is set as within \pm 6% of the directly weighed value. With as few as 39 participants completing the PortionSize and MyFitnessPal condition, we have at least 0.80 power to detect equivalence with \pm 6% error bounds (\pm 35.2 kcal). Additionally, with 39 participants completing the PortionSize and MyFitnessPal condition, we have power of 0.80 to detect a 46 kcal difference in error (effect size = 0.6) between the conditions. Finally, with 39 participants completing the PortionSize and MyFitnessPal condition, we have 0.80 power to detect an R^2 of 0.17, which is acceptable as studies with Bland-Altman analysis find that poor methods of measurement frequently have $R^2 \geq 0.16$.²²

Provisions to Monitor the Data to Ensure the Safety of Subjects

Adverse events will be monitored at each intervention visit. The PI and his co-investigators will review all data continuously to ensure the safety of each subject.

Withdrawal of Subjects

Subjects may be withdrawn from the study if he/she misses study visits and will be notified of their withdrawal via telephone or mail. If a subject voluntarily withdraws from the study, no additional data will be collected and they will be considered dropouts in the study.

Risks to Subjects

This study involves no greater than minimal risk. The main risk is breach of confidentiality, and the PBRC team will work to minimize this during data collection, handling, and analysis.

Potential Benefits to Subjects

Participants may benefit by increased awareness of their portion sizes with various food groups.

Sharing of Results with Subjects

The participants may receive information such as body weight and anthropometrics. Those results will be provided to the participant at the end of the study if requested.

Setting

The Ingestive Behavior, Weight Management, and Health Promotion Laboratory at Pennington Biomedical Research Center.

Compensation

Participants will receive \$75 for the successful completion of the study.

Provisions to Protect the Privacy Interests of Subjects

All attempts will be made to maintain a subject's privacy. Safeguards such as password-protected computers and networks have been put in place in order to limit access to subject data. Subjects will be given ample time to read over the consent, ask questions, and agree to participate in the research study. Subjects may decline to answer questions with which they are not comfortable. Each procedure will be explained to the subject before it is performed. We will always ensure the privacy of the subjects.

Participants will be advised to read the current version of the Privacy Statement for MyFitnessPal provided as a link within the consent form to understand how the company will use their information. The current version can be found here:

https://account.underarmour.com/en-us/privacy_and_terms

Compensation for Research-Related Injury

No compensation will be provided for research-related injury.

Economic Burden to Subjects

All study-related tests and procedures will be at no cost to the subject. The subject will incur transportation costs in getting to Pennington Biomedical Research Center. It is also possible that the subject will incur data charges by using their own smartphone during the study. The chances of this occurring can be mitigated by connecting their smartphone to WiFi while at the Center.

Consent Process

A designated and trained staff member will obtain informed consent during the first visit. Ample opportunity will be given for the subject to review the consent and ask any questions prior to signing the consent form. If subjects wish, they can take the form home and return at a different visit. We are aware that consent is an ongoing process.

References

4. Willett WC. *Nutritional epidemiology*. New York: Oxford University Press; 1998.

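### Between-app comparison only: the dependent t-test ignores the randomised visit order; a period term is a near-free improvement of minor expected benefit

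*Combined protocol and SAP*

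**What the plan says.** Under Participants and Recruitment, participants are "randomly assigned in approximately a 1:1 ratio to use PortionSize at the first visit (and MyFitnessPal at the second visit"), or the reverse order. Screening visit/Study Visit 1 confirms that each person uses both apps, one per visit: "in this within subjects design, participants will be randomized to use either PortionSize or my MyFitnessPal at this first visit". Study Visit 2 follows after about 3 to 14 days, with training on the other app: "They will then estimate food intake from another simulated lunch meal. This will be conducted exactly as Study Visit 1".

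Under Outcome measures, the between-app analysis is: "Differences in the observed error from PortionSize and MyFitnessPal will be compared with dependent t-tests". Error is the signed difference from weighed food. No period, visit or sequence term is given there. The exploratory regressions "will determine if error from the apps varies by body mass (kg, BMI), age, or sex"; visit order is not among the factors listed. The Power calculation section says "we have power of 0.80 to detect a 46 kcal difference in error (effect size = 0.6) between the conditions", based on "attrition of up to 10%, resulting in 39 participants finishing both visits".

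The analyses labelled primary, those "assessing equivalence between PortionSize and the criterion measures (and MyFitnessPal and the criterion measures), will rely on equivalence testing", are a separate question and outside this point.

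**The concern.** This is a two-sequence, two-period crossover. At the second visit everyone is estimating a simulated lunch for the second time, so average error could differ between visits whichever app is used. The plan randomises order but does not use order in the analysis.

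Two consequences follow if such a shift exists. It moves the paired difference in opposite directions in the two sequences, which inflates the estimated SD and widens the confidence interval for the app difference. If the sequences also finish with unequal numbers, the two shifts do not cancel fully and a small bias remains. What is at stake is some precision in the between-app comparison, which has its own power statement.

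**Working it through.** **Inputs from the protocol.** 43 recruited and 39 completers, so four dropouts; difference 46 kcal; effect size 0.6; stated power 0.80. Alpha 0.05 is stated for the equivalence tests. I assume it for the t-test too, two-sided, because sidedness is not given.

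**The plan's own figure.** Read as a paired effect size, 0.6 implies SD = 46/0.6 = 76.7 kcal. The noncentrality is 0.6 × √39 = 3.75 on 38 df, giving power 0.955, not 0.80. A paired test with 39 people has 0.80 power at effect size 0.460, that is, SD = 46/0.460, about 99.9 kcal (0.4604 before rounding). The protocol does not settle which SD is meant. That mismatch is a separate matter; here I carry both values.

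**Model.** Let τ be the true app difference (PortionSize minus MyFitnessPal error) and π the visit 2 minus visit 1 shift. The mean paired difference is τ − π for the n1 people using PortionSize first and τ + π for the n2 using it second.

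- *Unadjusted estimate:* τ + π(n2 − n1)/N, with a one-sample t on 38 df. Its estimated variance is about SD² + π² when the sequences are near-equal.
- *Adjusted estimate:* the simple average of the two sequence means, so π cancels. SE = (pooled SD/2) × √(1/n1 + 1/n2), on 37 df. At 19/20 and SD 76.7 this is 38.35 × 0.320 = 12.3 kcal.

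**Assumed π.** The protocol gives none. I use 20 to 60 kcal, about 3% to 10% of the 587 kcal meal implied by 35.2/0.06.

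**Power at τ = 46 kcal, completers split 19 and 20** (simulation, 200,000 runs per case). The paired unadjusted figures are for the residual bias running against or towards the app difference.

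| SD (kcal) | π (kcal) | Unadjusted, against / towards | Adjusted |
|---|---|---|---|
| 76.7 | 20 | 0.94 / 0.95 | 0.954 |
| 76.7 | 30 | 0.93 / 0.945 | 0.954 |
| 76.7 | 60 | 0.845 / 0.895 | 0.954 |
| 99.9 | 20 | 0.78 / 0.80 | 0.80 |
| 99.9 | 30 | 0.76 / 0.79 | 0.80 |
| 99.9 | 60 | 0.66 / 0.725 | 0.80 |

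At SD 76.7 and π = 30, the mean 95% CI half-width is 26.6 kcal unadjusted against 24.7 adjusted.

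**Bias at π = 30.** 30 × 1/39 = 0.8 kcal at 19/20; 30 × 5/39 = 3.8 kcal at 17/22.

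**Type I error, unadjusted, SD 76.7, π = 20/30/60.** 0.043/0.036/0.013 at 19/20 and 0.048/0.044/0.033 at 17/22. The visit shift inflates the estimated SD more than it disturbs the mean, so the test is conservative at these splits.

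**Likely splits.** Assuming a 21/22 start and four random dropouts, the chances (either direction) are 0.66 for 19/20, 0.30 for 18/21 and 0.05 for 17/22. No wider split is possible. The mean absolute imbalance is 1.79, so the mean absolute bias at π = 30 is 30 × 1.79/39 = 1.4 kcal.

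**The case against.** The strongest reply is that nothing here is an error. A paired t-test on a counterbalanced two-visit design is valid, and randomising the order already guards against order effects. The harm rests wholly on an assumed π. The design gives some reason to doubt a large one: people are trained on a different app at each visit, rate a different meal, and the weighing is covert, with no feedback on true values described. Because error is signed, practice might instead shrink errors towards zero or act differently by app, and a period term would not remove that. The 60 kcal case exceeds the 46 kcal difference used in the power calculation.

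Most of this stands, and it is why the point has the lowest severity. What remains is that counterbalancing removes bias only in expectation. It removes neither the extra variance nor the residual bias from unequal completers. The standard analysis does both for an additive shift, using a factor the trial already randomises.

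A reader might go further and infer that the planned test inflates type I error. A 15/24 split could do that if a visit effect exists, but nothing in the protocol leads to such a split. From a 21/22 start with four dropouts, the worst case is 17/22, where error stays below 0.05. If order were assigned by independent coin toss (no allocation method is stated), 15/24 or worse would have chance 0.20, but type I error averaged over all splits would still be 0.050.

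**Conclusion.** The point holds as a near-free improvement of minor expected benefit, limited to the between-app comparison. For an assumed π of 30 kcal at a near-equal split, the term recovers roughly 1 to 2 percentage points of power with SD 76.7 kcal and 1 to 4 with SD about 99.9 kcal. The gain is substantial only if the shift approaches or exceeds the 46 kcal difference itself. If there is no visit effect, there is no gain.

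Three stronger readings are not supported:

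- *The planned t-test is invalid or biased by design.* It is neither: order is randomised about 1:1.
- *Power is safe at 0.80, or alternatively fails, because of this omission.* Either answer depends on which SD is taken and on an unknown π. With SD 76.7, power at 19/20 stays above 0.80 over the range shown; with SD about 99.9 it falls below 0.80 in most cases.
- *The primary equivalence results are undermined.* Each app is tested against weighed food from the same visit, and that analysis is not at issue here.

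The figures assume normal paired differences, an additive shift common to both apps, a two-sided 0.05 test and 39 completers.

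**What to change.** For the between-app comparison, analyse completers' paired differences by the standard AB/BA method: the equal-weight average of the two sequence means, with pooled within-sequence SD on 37 df. An equivalent choice is a mixed model limited to the same completers, with fixed app and period and a random participant. Report the number of completers in each sequence. State that this removes an additive period effect only, not carry-over or an app-by-period interaction, and that the equivalence test of each app against weighed food is unchanged.

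The cost is a sentence or two of analysis wording and one degree of freedom, with no extra participants or data. With no visit effect, the power loss is about 0.001 at 19/20 (0.955 to 0.954 with SD 76.7; 0.800 to 0.799 with SD 99.9) and below 0.01 at 17/22 (to 0.951 and 0.793). At an unlikely 15/24 it would be 0.01 to 0.02 (to 0.944 and 0.778).

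### Does the stated equivalence power of at least 0.80 with 39 completers fail because it names no error SD and no true mean error?

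*Combined protocol and SAP*

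**What the plan says.** The Outcome measures section says that the primary analyses, for PortionSize and for MyFitnessPal each against directly weighed food, "will rely on equivalence testing using the Two One-side T-test (TOST"). The Power calculation section adds that the tests "will be used with alpha = 0.05 and specified acceptable lower and upper bounds of equivalence". The margin is ±6% of the weighed value, given as ±35.2 kcal.

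The same section plans for 43 recruits and says "we are powered even if we experience attrition of up to 10%, resulting in 39 participants finishing both visits". At that number, it says, "we have at least 0.80 power to detect equivalence with" the ±6% bounds. No SD and no assumed mean error go with this statement. The only information on variability is in the next sentence, about the comparison of the two apps: "we have power of 0.80 to detect a 46 kcal difference in error (effect size = 0.6) between the conditions". It does not say whether 0.6 is scaled by the SD of one app's error or by the SD of the paired difference.

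**The concern.** The power of a TOST depends on the SD of the errors and on the true mean error (bias). It peaks at zero bias and falls as the bias approaches the margin. A power quoted without either input cannot be checked, and the phrase about at least 0.80 could be taken as a guarantee that holds whatever the bias.

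The text also gives some reason to doubt zero bias in both apps. The Background says of self-report methods, food records among them, "The accuracy of these methods have been questioned", and describes MyFitnessPal as an app "which is an electronic food record".

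Taken as printed, 46/0.6 gives an SD of 76.7 kcal. If that is one app's error SD, the power is below 0.80 even at zero bias. At stake is the main analysis: an app that truly lies within ±6% might fail to be declared equivalent, and completers cannot be added afterwards.

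**Working it through.** **Inputs from the Power calculation section.** n = 39; margin m = 35.2 kcal; alpha 0.05, taken as 0.05 for each one-sided test; 46 kcal and effect size 0.6 for the between-app comparison. The implied meal is 35.2/0.06 = 586.7 kcal, so 1%, 2% and 3% mean error are 5.9, 11.7 and 17.6 kcal.

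**Method.** Let s be the SD of one app's error and b its true mean error. Equivalence is declared when the sample mean error ± t × (sample SD)/√39 lies wholly within ±35.2, with t = 1.686 on 38 df. Power is the probability of that event, taking the mean as normal and integrating over the chi-square distribution of the sample variance. A simulation of 200,000 runs at s = 76.7, b = 0 gave 0.759 against 0.758 by integration.

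**Can the plan's 0.80 be obtained?** At b = 0 and n = 39, power is 0.80 or more for s up to 73.8 kcal. The effect size is printed to one decimal, so 0.6 stands for 0.55 to 0.65 and 46/0.6 for 46/0.65 = 70.8 to 46/0.55 = 83.6 kcal.

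| Per-app SD (kcal) | 0% | 1% | 2% | 3% |
|---|---|---|---|---|
| 54.2 | 0.98 | 0.95 | 0.84 | 0.64 |
| 70.8 | 0.84 | 0.79 | 0.64 | 0.45 |
| 71.5 | 0.83 | 0.78 | 0.64 | 0.44 |
| 73.8 | 0.80 | 0.75 | 0.61 | 0.43 |
| 76.7 | 0.76 | 0.71 | 0.57 | 0.40 |
| 83.6 | 0.65 | 0.61 | 0.49 | 0.35 |

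**Does one SD fit both power statements?** Try s = 71.5 kcal. The effect size is 46/71.5 = 0.643, which rounds to 0.6.
- TOST at zero bias: 0.83.
- The 46 kcal comparison, two-sided 0.05, as independent samples with 39 per group: noncentrality 0.643 × √(39/2) = 2.84, power 0.80.
- The same comparison as a paired test with uncorrelated errors: SD of differences 71.5 × √2 = 101.1, noncentrality 46 × √39/101.1 = 2.84, power 0.79.

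So one per-app SD, consistent with the printed figures, supports both statements to within rounding.

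**The other reading of 0.6.** If 76.7 kcal is the SD of paired differences, and the two apps have equal SDs and uncorrelated errors, one app's SD is 76.7/√2 = 54.2 kcal. TOST power is then 0.98 at zero bias and stays at 0.80 up to 13.2 kcal (13.2/586.7 = 2.3%). At this SD of differences, zero-bias power falls below 0.80 only once the correlation exceeds 0.46. This reading does not reproduce the between-app figure, since a paired effect size of 0.6 with n = 39 has power 0.955.

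**Is 0.80 always lost before half the margin?** Holding 0.80 at 17.6 kcal needs s of at most 43.4 kcal. With equal SDs and non-negative correlation, neither reading gives an SD that low. With unequal SDs one can. If the SD of differences is 76.7 and the errors are uncorrelated, one app may have SD 43 and the other √(76.7² − 43²) = 63.5. The app with SD 43 has power 0.81 at half the margin.

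**The case for a change.** The best case for a change is that the two missing inputs are the ones that drive the result, and that the reserve is thin on the reading that fits both power statements. At an SD of 70.8 to 73.8 kcal, an app with a 2% mean error, well inside the margin, would be declared equivalent with probability only 0.61 to 0.64. Keeping 0.80 there would take 58 to 63 completers, more than the 43 to be recruited. At 76.7 kcal exactly, even zero bias gives 0.758, and 0.80 would take 42 to 43 completers (0.7998 at 42, 0.812 at 43), which uses up the attrition allowance.

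The arithmetic stands, and so does the observation that the SD and the mean error are not written down. Three things limit what follows:

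- The phrase about at least 0.80 is tied to having as few as 39 completers. It is a floor over the number of completers, not over bias.
- The shortfall at 76.7 kcal disappears within the rounding of 0.6.
- No section names a mean error at which 0.80 must be kept. A target of 1% or 2% would be the reader's preference, and the extra recruitment would rest on an SD that the documents do not give. At 57.8 kcal or less, 39 completers already hold 0.80 up to 2%.

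The Background's remark is about self-report methods in general and gives no size of bias for trained users rating simulated laboratory meals. The 46 kcal is a difference to be detected, not a forecast of either app's error.

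**Conclusion.** The concern does not call for a change. The stated power is attainable with 39 completers at zero mean error for any per-app SD up to 73.8 kcal, and it is 0.83 at 71.5 kcal, a value that agrees with the plan's own 46 kcal and 0.6. The fall in power with bias is a property of every TOST and not an error in this plan.

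What remains is missing detail in the power paragraph: the per-app SD, the assumed mean error (presumably zero) and the SD that defines 0.6. Supplying it would alter neither the test, the margin nor the validity of a conclusion of equivalence. If a test fails, the observed mean error and its confidence interval will show whether bias or imprecision was the cause.

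This rests on 0.05 for each one-sided test, normally distributed errors, and zero mean error as the planning default. With 0.025 per side every power would be lower (0.596 instead of 0.758 at 76.7 kcal and zero bias), but the plan states 0.05. The sponsor's own SD is unknown, so the true reserve could be larger or smaller than the table shows.
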